13.1 Primary Analysis

The percentage of study eyes gaining at least 15 letters in BCVA from baseline will be summarized using discrete summary statistics, including exact 90% and 95% CIs by phase and treatment group.

Treatment group comparisons for study eye will be completed using:

- Fisher's exact statistic:
Example SAS codes: PROC FREQ Data=xx;
Weight count / ZEROS;
Tables aa*treatment / FISHER;
Run;
where aa indicates Yes/No whether at least 15 letters gained.
- Exact 90% and 95% CIs using the Farrington-Manning score statistic:
Example SAS codes: PROC FREQ data=xx;
tables = aa*treatment/ riskdiff(cl=fm);
Weight Count ;
Run;
where aa indicates Yes/No whether at least 15 letters gained.

- Exact logistic regression will be utilized to determine treatment effect on the percentage of study eyes gaining at least 15 letters in BCVA from baseline after adjusting for baseline BCVA. Odds ratio and 95% CI will be presented.

Example SAS codes: PROC LOGISTIC data=xxx descending ;

(e.g., to model probability of at least 15 letters change in BCVA; y-variable="Y");

Class treatment;

Model xx = treatment baseline_BCVA;

Exact treatment baseline_BCVA / estimate = both;

Run;

These analyses will be used to determine differences in formulations and to assess whether there are differences in outcomes.

The efficacy summaries will be performed on the ITT population:

- using LOCF (for continuous variables);
- imputing missing as failure (for categorical variables); and
- using observed data only.

Subjects who receive rescue medication prior to the summarized visit will be imputed as failures for the summarized visits. No additional imputation methodologies will be performed in this early phase study.

The percentage of subjects gaining or losing at least 15 letters at other study visits and the percentage of subjects gaining or losing at least 10 letters at each study visit will be analyzed similarly.

Change from baseline in BCVA letters to each follow-up visit will be summarized using continuous summary statistics, including 90% and 95% CIs by treatment group.

Box plot of change from baseline in BCVA letter score by visit and treatment group for study eye will be presented. Separate box plot of change from baseline in BCVA letter score for study eye will be presented for subjects with improvement of 15 or more letters, 10 or more letters, and 5 or more letters.

A linear model with change from baseline BCVA letters for study eye only as the response, baseline BCVA letters as a covariate, and treatment group as a main effect will be fit to determine treatment group effect with separate models completed for each follow-up visit. These analyses will be used to determine differences in formulations and may be used to assess whether there are differences in outcomes between subjects' data pre- and post-interim to determine whether the data may be pooled. Subjects who receive rescue medication prior to the summarized visit will have their measure replaced with their last observation prior to receiving rescue medication. The least squares mean, standard error, and CI for each treatment group, and the difference between treatment groups will be presented for

study eye only. Additionally, analyses will be completed using individual two-sample t-tests and 90% and 95% CIs around the difference between treatment groups in mean BCVA and mean change from baseline BCVA for study eye only.

Median time (in months) to achieve a treatment response of ≥ 15 letters improvement from baseline in BCVA for study eye and median time (in months) to rescue therapy will be estimated using Kaplan-Meier methods with 90% and 95% CI, calculated using the method of Brookmeyer and Crowley (1982). The log rank statistic will be used to determine differences in time to achieve response between the two treatment groups to determine differences in formulations. Cox proportional hazards will also be used to analyze time to event, including baseline BCVA as a covariate. Results from unscheduled visits or early termination visits will be included in the time to event analysis.

For the event of achieving a treatment response of ≥ 15 letters improvement from baseline in BCVA for study eye, the starting date will be the date of first dose. Subjects receiving rescue medications prior to or on the same date as the achievement of improvement will be considered censored on the day of rescue medication receipt; subjects with neither rescue medications received nor improvement achieved will be considered censored on the last date known to be rescue medication free and improvement achievement free. For the event of receiving rescue therapy, the starting date for the time to event evaluation will be the date of first dose. Subjects who do not receive rescue therapy will be considered censored on the last date known to be event free.

Example SAS codes: PROC LIFETEST Data=xxx method=KM;

Strata treatment/test=logrank;

Time AVAL*CENSOR(0);

Run;

where CENSOR indicates censored subjects.

PROC PHREG Data = xxx;

Class Treatment (param=ref ref='CF2');

model AVAL*CENSOR(0) = baseline_BCVA Treatment/ties=exact;

run;

where CENSOR indicates censored subjects.

In all analyses, data from subject visits after receipt of rescue medication will be imputed using last observation prior to receiving rescue medication for continuous endpoints and will be imputed as failures for success/failure variables.

Additionally, a subset of the efficacy analyses will be performed by combining the initial phase subjects with the randomization phase subjects.

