| 
18. Currently using or anticipating the use of systemic corticosteroids during the study (with the exception of inhaled, intranasal or topical corticosteroids, providing the dose has remained stable for the 1-month prior to Visit 1, and it is not anticipated to change during the course of the study)
 
19. Any clinically significant or uncontrolled serious or severe medical or psychiatric condition
 
20. Participation in any other clinical study within 30 days prior to Visit 1
 
21. History of hypersensitivity or poor tolerance to any components of the preparations to be used in this study such as dexamethasone or biodegradable polymer (poly D, L-lactic co-glycolic acid, PLGA) excipients or fluorescein
 
22. Systemic condition that may confound the study outcome per the investigator's opinion (e.g. uncontrolled diabetes [i.e. glycosylated hemoglobin (HbA1c) level >12], uncontrolled hypertension [e.g. ≥160/100 mmHg], treatment for a serious systemic infection, history of cerebral vascular accident or myocardial infarction within 6 months prior to screening, renal failure requiring dialysis or renal transplant, cancer or other conditions)
 
23. Women of childbearing potential, or male subjects with a female partner of child-bearing potential who are pregnant, nursing, planning a pregnancy, or not using a medically acceptable form of birth control. An adult woman is considered to be of childbearing potential unless she is one year post-menopausal or 3 months post-surgical sterilization. Male subjects with a female partner of child-bearing potential must have had a prior vasectomy or agree to use an effective method of birth control during the treatment period and for three months after the subject has completed the study. All females of childbearing potential must have a negative urine pregnancy test result at the screening examination and must not intend to become pregnant during the study.
 |
|---|

Study Population:

A total of approximately 45 subjects will be enrolled into the study at approximately 20 investigational sites within the United States, comprising a total of approximately 25 subjects treated with AR-1105-CF1 (up-to 5 in the initial phase and 20 in the randomized phase), and 20 subjects treated with AR-1105-CF2 (randomized phase only). Subjects will be at least 18 years of age with a diagnosis of ME secondary to RVO, each of whom meets all the inclusion criteria and none of the exclusion criteria.

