2.4 Statistical Hypotheses

The statistical analysis of primary efficacy variable is conducted to gain information for future studies.

The percentage of study eyes gaining at least 15 letters in BCVA from baseline will be summarized using discrete summary statistics, including exact 90% and 95% confidence intervals (CIs) by treatment group. Treatment group comparisons will be completed using Fisher's exact test.

Treatment group comparisons based on the 90% and 95% CIs using the Farrington-Manning score test will be completed.

$$H_0: p_1 - p_2 = 0$$

$$H_1: p_1 - p_2 \neq 0$$

where H_0 denotes the null hypothesis, and H_1 denotes the alternate hypothesis; p 's denote the proportion of eyes gaining at least 15 letters for each treatment.

3. Study Design and Procedures

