8.4 Data Analysis Conventions

All data analyses will be performed by SDC. Statistical programming and analyses will be performed using SAS® Version 9.4 or higher. Output will be provided in rich text format (RTF) for tables and portable document format (PDF) for tables, listings, and figures using landscape orientation. All study data will be listed by treatment (and phase [initial vs randomized] for CF1), subject and visit (as applicable).

Summaries for continuous and ordinal variables will include the number of observations (n), arithmetic mean, standard deviation (SD), median, minimum, and maximum. Minima and maxima will be reported with the same precision as the raw values; means and medians will be presented to one additional decimal place than reported in the raw values. Standard deviations will be presented to two additional decimal places than reported in the raw values. Summaries for discrete variables will include number and percentages. All percentages will be rounded to one decimal place (i.e., XX.X%). Change from baseline will be calculated as follow-up visit minus baseline.

All statistical tests will be two-sided with a significance level of 0.05 ($\alpha = 0.05$) unless otherwise specified. Confidence intervals for differences between treatment groups will be two-sided at 90% and 95% confidence. All p-values will be rounded to four decimal places; p-values less than 0.0001 will be presented as "<0.0001"; p-values greater than 0.9999 will be presented as ">0.9999."

Unless otherwise specified, summaries will be presented by treatment group and, where appropriate, visit.

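### The example SAS code for the responder comparison in SAP 13.1 transposes the table and requests neither exact nor 90% limits, so it does not carry out the section's own prose

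*SAP*

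**What the plan says.** SAP 2.4 sets the null hypothesis as p1 − p2 = 0, where the p's "denote the proportion of eyes gaining at least 15 letters for each treatment". The contrast is therefore between formulations, each with its own responder proportion. It does not say which formulation is p1.

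SAP 13.1 lists among the comparisons "Exact 90% and 95% CIs using the Farrington-Manning score statistic". SAP 8.4 repeats the two levels: "Confidence intervals for differences between treatment groups will be two-sided at 90% and 95% confidence".

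The example code under that bullet is "tables = aa*treatment/ riskdiff(cl=fm", and aa is defined there as whether at least 15 letters were gained. The block has no EXACT statement and no ALPHA= option. The exact logistic regression example in the same section does request an exact analysis ("Exact treatment baseline_BCVA / estimate = both"), under a bare "Class treatment" statement. The PHREG example later in 13.1 sets reference coding with CF2 as the reference level.

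The 10-letter endpoints, the worsening endpoints and the other visits are to be analysed in the same way. SAP 13.1 adds that "a subset of the efficacy analyses will be performed by combining the initial phase subjects with the randomization phase subjects"; the Protocol synopsis expects "approximately 25 subjects treated with AR-1105-CF1 (up-to 5 in the initial phase and 20 in the randomized phase" and 20 on CF2.

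**The concern.** The RISKDIFF option of PROC FREQ contrasts the rows of a two-way table within a column. With the outcome in the rows, it compares the share of one formulation among responders with its share among non-responders. That is a different quantity from p1 − p2, and the ratio between the two depends on how many eyes responded. Neither relabelling nor a change of sign recovers the intended figure.

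Without an EXACT request and an alpha setting, the block returns one large-sample interval at the default 95% level. The prose promises exact intervals at two levels.

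The stray = in the TABLES statement has to be removed before the block will run. If a programmer removes only that, the report would show a difference and interval that do not belong to the two percentages beside them. The study makes no power claim for efficacy, so the estimate and its interval are the informative part of this comparison. Protocol 3.1 says efficacy signals will help choose the formulation to develop.

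**Working it through.** **Inputs.** 20 evaluable eyes per group (SAP Section 5); 25 and 20 when the phases are combined (Protocol synopsis); the contrast p1 − p2 (SAP 2.4). The plan attaches no numerical result to this comparison and gives no response rates, so there is no figure to reproduce and all responder counts below are assumptions. SAS behaviour is taken as standard. Score intervals were computed in Python by inverting the score statistic with restricted maximum likelihood estimates.

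**1. Size of the transposition.** Let a of n1 respond on CF1 and c of n2 on CF2, with m = a + c and N = n1 + n2. The coded layout gives

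a/m − (n1 − a)/(N − m) = (a·n2 − c·n1)/(m(N − m)) = (a/n1 − c/n2) × n1·n2/(m(N − m)).

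The sign depends on which column is reported, in either layout, and is set aside here.

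| Total responders m | Factor, 20 v 20 |
|---|---|
| 20 | 400/(20×20) = 1.00 |
| 16 | 400/(16×24) = 1.04 |
| 12 | 400/(12×28) = 1.19 |
| 10 | 400/(10×30) = 1.33 |
| 6 | 400/(6×34) = 1.96 |
| 4 | 400/(4×36) = 2.78 |

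For 25 v 20 the factor is 500/(22×23) = 0.99 at m = 22, 500/(14×31) = 1.15 at 14, 500/(7×38) = 1.88 at 7 and 500/(4×41) = 3.05 at 4.

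**2. Worked cases** (percentage points, large-sample 95% score interval):

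| Assumed counts | Intended difference | Coded difference |
|---|---|---|
| 8/20 v 4/20 | 20.0 (−8.6 to 45.9) | 8/12 − 12/28 = 23.8 (−9.8 to 51.2) |
| 5/20 v 1/20 | 20.0 (−2.6 to 43.0) | 5/6 − 15/34 = 39.2 (−4.1 to 62.2) |
| 10/25 v 4/20 | 20.0 (−7.5 to 44.0) | 10/14 − 15/31 = 23.0 (−8.4 to 48.2) |

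One true difference of 20 points thus prints as three different values.

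**3. What the transposition leaves alone.** Fisher's p-value does not depend on orientation (0.3008 for 8/20 v 4/20 both ways). At zero difference the pooled variance is m(N − m)/(N·n1·n2) in the intended layout and n1·n2/(N·m(N − m)) in the coded one. Their ratio is the square of the factor above, so z is identical: 1.3801 for 8/20 v 4/20 and 1.7712 for 5/20 v 1/20. A check of every outcome except none or all responding, at both levels, found no change in whether zero is excluded: (21×21 − 2)×2 = 878 checks at 20 v 20 and (26×21 − 2)×2 = 1,088 at 25 v 20.

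**4. What the missing exact request can change.** Take 5/20 v 1/20 in the intended layout. The large-sample 90% interval, 1.7 to 39.2, excludes zero. The exact unconditional score interval, −0.3 to 41.6, includes it. The one-sided p at zero is 0.0383 large-sample and 0.0533 exact, against 0.05. Among 20 v 20 outcomes favouring CF1 whose large-sample interval excludes zero, the exact interval includes it in 6 of 136 at 90% and 2 of 121 at 95%. These are counts of possible tables, not probabilities.

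**5. Logistic coding (clarification only).** Under default effect coding, the exponentiated treatment parameter for two groups is the square root of the odds ratio. For 8/20 v 4/20 the unadjusted odds ratio is (8/12)/(4/16) = 2.67, and √2.67 = 1.63 would be printed.

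**The case against.** The strongest reply is that the plan prescribes nothing wrong. The hypothesis, the method and both levels are correct in the prose, and the blocks are headed as examples with placeholder names. Harm requires someone to repair the syntax, keep the layout, overlook the bullet heading directly above it, and not compare the output with the arm percentages. The examples are sketches elsewhere too: the LIFETEST block has no alpha setting although 90% and 95% limits are promised for the medians. The absence of ALPHA= is therefore weaker evidence of a contradiction than the transposition or the missing exact request.

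Much of this stands and limits the weight of the point. With 12 to 20 responders out of 40, the factor is only 1.00 to 1.19. Factors of 2 to 3 need few events. Worsening could be such an outcome, but missing and rescued eyes are imputed as failures, which might raise those counts. The SAP lists no combined-phase table and does not say which BCVA tables will show a risk difference. The logistic coding is not an error against the text, because the prose names no reference level.

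What does not stand is that the example label settles the matter. This is the only code given for the risk difference, it must be edited in any case, and as laid out it estimates another quantity.

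**Conclusion.** The mismatch is real and minor. Read under standard PROC FREQ behaviour, the block estimates the wrong contrast and yields a single large-sample 95% interval where exact 90% and 95% intervals are promised. For the assumed counts, a true 20.0 points prints as 23.0 to 39.2. The transposition does not alter whether zero is excluded; the missing exact method occasionally can. No sample size, error rate or analysis population changes, the primary variables are safety variables, and a check against the two responder percentages would reveal the transposition. The conclusion rests on SAS behaviour that the documents do not describe and that was not run. The numerical sizes rest on assumed counts, but the algebraic factor does not.

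**What to change.** In the risk-difference block of SAP 13.1:

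- Write `tables treatment*aa` without the =, and name the column for eyes that gained.
- Add an EXACT RISKDIFF request using the score method.
- Run it at ALPHA=0.05 and ALPHA=0.10.

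State in SAP 2.4 which formulation is p1. As a clarification, give the CLASS statement in PROC LOGISTIC the same reference coding that the PHREG example already uses.

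The cost is a few lines of example code and one phrase. Exact intervals are somewhat wider: for 8/20 v 4/20 the 95% width goes from 54.5 to 56.7 points, and for 5/20 v 1/20 the 90% width goes from 37.6 to 42.0 points. The prose already commits to that price.

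### The example exact logistic code sets no reference coding or reference level for treatment, so as written it does not deliver the CF1:CF2 odds ratio that SAP 13.1 promises

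*SAP*

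**What the plan says.** SAP 13.1 (Primary Analysis) sets out the adjusted responder comparison: "Exact logistic regression will be utilized to determine treatment effect on the percentage of study eyes gaining at least 15 letters in BCVA from baseline", with adjustment for baseline BCVA. The reported quantity is also stated: "Odds ratio and 95% CI will be presented".

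The example code for this step has three working lines:
- "Class treatment", with no coding option and no reference level;
- "Model xx = treatment baseline_BCVA";
- "Exact treatment baseline_BCVA / estimate = both".

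No further statement in that code asks for a CF1 v CF2 contrast from the exact fit. Later in the same section, the Cox example gives both the coding and the reference level: "Class Treatment (param=ref ref='CF2". SAP 8.4 names the software: "Statistical programming and analyses will be performed using SAS® Version 9.4 or higher". Protocol 9.6.2 plans the same exact logistic regression without code, and SAP section 1 says that the SAP's methods supersede the protocol's. The SAP example is therefore the only place where coding for this model could have been set.

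**The concern.** An odds ratio obtained by exponentiating a model parameter compares the two formulations only if treatment is coded one unit apart, as 1 and 0. If treatment is coded +1 and -1, the groups are two units apart and the parameter is half the log odds ratio. The logistic code leaves this choice to the software default and also leaves open which formulation is the numerator. The Cox code shows that the authors set both when they thought of it.

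This is the only baseline-adjusted estimate for the responder proportion at Month 6. SAP 13.1 applies the same methods to the 10- and 15-letter gains and losses at the other visits, so a coding fault would recur there. The protocol uses efficacy signals, together with safety, to choose a formulation, and says that the study will inform the design and power of later studies. For the second purpose the size of the odds ratio and the width of its interval matter more than the p-value.

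**Working it through.** The plan gives no odds ratio to reproduce. Its only computed figure, the 13.9% bound for an event not seen in 20 subjects, reproduces as 1 - 0.05^(1/20) = 0.1391, but has no bearing on this point.

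**Inputs.** From the documents: two groups, 1:1, 20 evaluable per group; baseline BCVA of 25 to 70 letters; two-sided 0.05 (SAP 8.4: "All statistical tests will be two-sided with a significance level of 0.05"). Assumed, because the documents give no responder rates: the counts used below. Also assumed: the software's default coding, for which both possibilities are shown.

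**Algebra.** Let x = 1 for one formulation and 0 for the other (reference coding), and z = 2x - 1 (effect coding). Exact logistic regression conditions on the number of responders s and on the sum of baseline BCVA among responders. The sufficient statistic for treatment is T = sum of x over responders, or U = sum of z over responders = 2T - s. With s fixed, the conditional probability of each outcome is proportional to exp(β_z × U), which is proportional to exp(2β_z × T). Hence β_z = β_x / 2. The tail probabilities that define the exact limits are the same sets of outcomes under both codings, so both limits are also halved on the log scale. At β = 0 the two distributions coincide, so the exact p-value is identical. After exponentiation, the estimate and both limits become square roots.

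**Simple case, unadjusted Wald, for scale (assumed 8/20 v 4/20).**
- Odds ratio = (8 × 16)/(12 × 4) = 2.67; log = 0.981.
- SE = sqrt(1/8 + 1/12 + 1/4 + 1/16) = 0.722.
- 95% limits on the log scale: 0.981 ± 1.96 × 0.722 = -0.434 and 2.395, that is 0.65 and 10.97.
- Halved: 0.490, -0.217 and 1.198, that is 1.63 (0.81 to 3.31).
- z = 0.981/0.722 = 1.36 and p = 0.174 under both codings.

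Likewise an odds ratio of 4 would become 2.

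**Exact conditional logistic regression, adjusted, with simulated baseline BCVA in 5-letter steps from 25 to 70.**

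| Assumed responders | Reference coding: OR (95% CI) | Effect coding: exp(β) (95% CI) | Exact p, both |
|---|---|---|---|
| 9/20 v 4/20 | 3.34 (0.65 to 20.6) | 1.83 (0.81 to 4.54) | 0.155 |
| 8/20 v 3/20 | 3.53 (0.68 to 24.7) | 1.88 (0.82 to 4.97) | 0.157 |
| 12/20 v 6/20 | 3.03 (0.70 to 14.2) | 1.74 (0.84 to 3.77) | 0.111 |

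In the first row the log-scale CI width falls from 3.45 to 1.73. The crude odds ratio there is (9 × 16)/(11 × 4) = 3.27, close to 3.34 and far from 1.83, so a comparison with the 2x2 table would expose the wrong scale. The square-root relation does not depend on the assumed counts or baselines.

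**Range over the software assumption.** If the default is reference coding, the scale is right and only the reference level is left unstated. If it is effect coding, the exact odds ratio is either withheld or appears as its square root.

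**The case against.** The strongest objection is that the documents say nothing about how the procedure codes a CLASS variable by default, or what it prints when reference coding is absent. The calculation shows what follows from +1/-1 coding, not that the software uses it. This stands, and it limits the certainty of the point. It does not remove the gap in the text: the coding and the reference level are unset here and set in the Cox example.

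Second, the code is headed as an example, uses placeholder names and has a prose remark inside the procedure step, so it is not the production program. The governing sentence promises an odds ratio, and a program returning its square root would not comply with it. This also stands, and a careful programmer may well correct the line.

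Third, the primary objective is safety, the study is not powered for efficacy, and no decision rule uses this odds ratio. The linear and Cox models, which also adjust for baseline BCVA, are not touched. The crude 2x2 table behind the Fisher and Farrington-Manning results is there for comparison. All of this lowers the weight of the point.

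A reader might go further and infer that the trial will report an adjusted effect and CI pulled toward 1. The documents do not support that: it needs the unconfirmed default, it needs the second of two mutually exclusive outcomes, and it needs the example code to be run unchanged.

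**Conclusion.** The point holds as a specification fault in SAP 13.1. The exact logistic example sets neither coding nor reference level for treatment, so as written it does not deliver the promised CF1:CF2 odds ratio, and it is inconsistent with the Cox example in the same section. On the assumption that the default is effect coding, the consequence is exact: the log odds ratio and both limits are halved. The exact odds ratio is then either missing or replaced by its square root, with a log-scale CI half as wide as it should be.

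Inference is not affected. The p-value, the side of 1 on which the estimate falls for a given contrast, and whether the CI includes 1 are the same under either coding. It is worth correcting before the analysis is programmed, but it does not threaten the study's conclusions on safety or its other efficacy models.

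**What to change.** Add the options `param=ref ref='CF2'` to the treatment CLASS statement in the exact logistic example, matching the Cox example. State in the text of SAP 13.1 that the odds ratio is CF1 relative to CF2. Run the example on a small test data set to confirm what the exact output contains, and check the exact odds ratio against the crude 2x2 odds ratio; a result near the square root of the crude value signals the wrong coding. Carry the same line into the programs for the other responder endpoints and visits. The cost is one code option and one sentence, with no effect on conduct, data collection or the test.

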Within the last 10 years, intravitreal pharmacotherapy has revolutionized the therapeutic options for ME-associated retinal vascular diseases, and particularly for RVO. Current options for treating ME depend upon the cause and severity of the condition. In the case of RVO, the goal is to reduce the amount of fluid leakage and decrease the edema, thus leading to improved visual acuity (VA). Argon laser photocoagulation was used for many years to treat ME associated with BRVO, but was less effective in the treatment of CRVO, and was not successful in all patients ([Fekrat 1997](#)). Currently, two classes of medication are approved to treat ME following RVO – corticosteroids (such as OZURDEX® dexamethasone intravitreal implant), and more recently, anti-vascular endothelial growth factor (VEGF) therapies such as ranibizumab (LUCENTIS®) and afibbercept (EYLEA®). The anti-VEGFs, while effective at modulating vascular permeability, do not address the inflammatory component of RVO however. Corticosteroids have the advantage of targeting the three components of the pathophysiology of RVO; reducing ME through inhibition of multiple inflammatory mediators, stabilizing the blood brain barrier and decreasing vascular permeability ([Zas 2017](#), [OZURDEX PI](#)). Corticosteroids such as dexamethasone (OZURDEX) and triamcinolone (KENALOG®) have demonstrated ME reduction and improvement in VA when dosed intravitreally ([Cekic 2005](#), [Ip 2003](#), [OZURDEX PI](#)). OZURDEX (0.7 mg dexamethasone) intravitreal implant has been evaluated in RVO and demonstrated efficacy up to 6 months ([Haller 2010](#)), although the peak efficacy is generally achieved by Month 3 ([Joshi 2013](#), [Bandello 2015](#)).

While both classes of medication have demonstrated efficacy in RVO patients, the treatment burden is high, with the anti-VEGFs typically requiring monthly ([LUCENTIS PI](#), [EYLEA PI](#)) intravitreal injections, and the dexamethasone intravitreal implant typically requiring re-injection every 3 months ([Bezatis 2013](#), [Augustin 2014](#)). A corticosteroid implant that offered a longer duration of effect would provide the benefit of reducing the

treatment burden on patients while treating the inflammatory components of ME that are not addressed by inhibition of VEGF.

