3.2 Rationale for Study Design and Control Group

While current treatment options for RVO are effective for many patients, the treatment burden is high. This study is designed to enable selection of the optimal AR-1105 formulation to continue with further clinical development. The optimal formulation will provide strong efficacy and a long duration of effect. The hypothesis is that a longer (>3 months) sustained release should necessitate less frequent intravitreal injections, and a lower steroid dose would potentially result in fewer, or less-frequent steroid-associated AEs without compromising effectiveness. Taken together these attributes would reduce the burden of treatment. The study is designed to inform decisions on further development of AR-1105 as safely and efficiently as possible.

[figure not shown]

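### Continuous BCVA and CRT are analysed only by LOCF and observed data, with neither named as main; both can mislead at Month 6, and a repeated-measures model should be added as the main analysis

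*SAP*

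**What the plan says.** SAP 13.1 gives three rules for missing efficacy data in the ITT population:

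- continuous variables: "using LOCF (for continuous variables";
- categorical variables: "imputing missing as failure (for categorical variables";
- a further version "using observed data only".

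It then closes the list: "No additional imputation methodologies will be performed in this early phase study". Change from baseline in BCVA is analysed by a baseline-adjusted linear model, "with separate models completed for each follow-up visit", together with two-sample t-tests. SAP 13.1 says these models serve to determine differences between the formulations. SAP 13.2 carries the same approaches over to CRT.

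The table list in SAP Section 20 pairs an LOCF table with an observed-case table for BCVA (14.2.1.2.1 and 14.2.1.2.2) and for CRT (14.2.2.1.1 and 14.2.2.1.2). None of these is marked as the main one.

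SAP 13.1 has a separate rule for rescued subjects. In all analyses, their later data "will be imputed using last observation prior to receiving rescue medication for continuous endpoints".

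On purpose, Protocol 3.2 says: "The optimal formulation will provide strong efficacy and a long duration of effect". Protocol 3.1 says that data through Month 6 will determine which formulation goes forward.

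**The concern.** LOCF sets a leaver's Month 6 value equal to the last value seen, so it assumes no change after exit. How long the effect lasts is one of the things this trial is meant to find out. For the marketed dexamethasone implant, Protocol Section 1 reports efficacy up to 6 months, "although the peak efficacy is generally achieved by Month 3". If AR-1105 behaved in that way, a subject last seen near the peak would bring a peak value to Month 6. The arm with more such exits would then look more durable.

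The observed-case tables do not fully cover this. Each per-visit model uses only the subjects present at that visit and ignores what leavers showed earlier. If poorer responders leave more often, those who remain are a favourable selection. The two planned versions could then err in the same direction, and their agreement would be falsely reassuring.

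At stake are the Month 6 continuous means and arm differences. They feed formulation selection and, according to SAP Section 5, the design and power of later studies.

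**Working it through.** **Inputs.** The documents give about 20 subjects per arm (Protocol 9.2, SAP Section 5) and efficacy evaluations at Months 1 to 6. The only figure stated in the sample-size sections is the 13.9% adverse-event bound. It reproduces as 1 − 0.05^(1/20) = 0.139 but says nothing about BCVA or CRT. No dropout rate, SD or AR-1105 time course is given, so the rest is assumed: mean gains of 8, 10, 10, 8, 6 and 4 letters at Months 1 to 6, SD 12, between-visit correlation 0.7, leavers last seen at Month 2, 3 or 4, and no true arm difference.

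**1. LOCF, random dropout.** Bias in an arm's Month 6 mean = dropout × (mean at last visit − mean at Month 6).

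- Mean at last visit = (10 + 10 + 8)/3 = 9.33, so the fade is 9.33 − 4 = 5.33 letters.
- 15% in both arms: 0.15 × 5.33 = 0.80, so the LOCF mean is 4.8 against a true 4.0 (simulated: 4.7 to 4.8).
- 25% v 5%: 4 + 1.33 = 5.3 and 4 + 0.27 = 4.3. The false difference is 0.20 × 5.33 = 1.1 letters (simulated means 5.4 and 4.3, difference 1.1).

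**2. The alternatives at 25% v 5% dropout.** Simulated false arm difference at Month 6, in letters:

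| Dropout | LOCF | Observed-case | Likelihood model |
|---|---|---|---|
| Unrelated to outcome | 1.1 | about 0 | about 0 |
| Poorer responders leave more often | about 0.5 | 0.9 to 1.2 | about 0 |

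The second row uses a nominal 25% v 5%. Its exact values depend on how strongly exit is tied to response.

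**3. Direction.** The sign depends on the time course and on when subjects leave.

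- Effect sustained at 10 letters from Month 2, 25% v 5% random dropout: LOCF difference 0.00.
- Effect 4 letters at Day 8 and 10 at Month 6, exits after Day 8, 20% v 5%: 0.20 × (4 − 10) = −1.2 and 0.05 × (4 − 10) = −0.3. The false difference is −0.9 letters.

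**4. Range.** Per-arm LOCF bias = dropout × fade, in letters:

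| Dropout | Fade 3 | Fade 5 | Fade 10 |
|---|---|---|---|
| 10% | 0.3 | 0.5 | 1.0 |
| 20% | 0.6 | 1.0 | 2.0 |
| 30% | 0.9 | 1.5 | 3.0 |

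For CRT, an assumed fade of 50 to 150 µm with 20% dropout gives 10 to 30 µm per arm. With 20% v 5% dropout, the false difference is 0.15 × 50 = 7.5 to 0.15 × 150 = 22.5 µm.

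**5. Scale.** With SD 12, the standard error of an arm difference is 12 × √(2/20) = 3.79, and the 95% half-width is 2.024 × 3.79 = 7.7 letters (6.4 for SD 10, 9.6 for SD 15). In the random 25% v 5% case, the LOCF test has a type I error of about 5.9% against a nominal 5%.

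**6. What LOCF does not reach.** The Month 6 endpoint of at least 15 letters gained counts missing as failure. Time to response, time to rescue and the two macular-edema analyses use Kaplan-Meier censoring. Conversely, the post-rescue rule puts carried-forward values into the observed-case tables as well.

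**The case against.** The strongest reply is that the plan already contains the remedy. With random dropout, the observed-case table is as free of bias as a likelihood model, and a reader would see it diverge from the LOCF table. That stands for random dropout, but not when leaving depends on response.

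The errors are small beside the sampling error, the trial is expressly not powered for efficacy, and safety is its primary objective. That stands too, and it limits the weight of the point. It does not remove it, because an unpowered study is read through its point estimates.

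A reader might infer that LOCF is bound to overstate durability and to favour the arm with more dropout. The documents do not support this. The Month 3 peak in Protocol Section 1 describes the marketed implant. AR-1105 is designed to last longer and has had no human exposure, and the bias vanishes or reverses under other plausible time courses. Under Protocol 6.10.2, the Month 6 assessments are also attempted at withdrawal, so the last value may fall after the peak, although it is still not a Month 6 value. The last pre-rescue value need not be a peak either: the guideline criteria in Protocol 3.1 describe worsening against baseline.

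Per-visit models are valid in themselves. Their weakness is that they set aside earlier data from subjects missing at that visit. SAP Section 1 allows supplementary analyses to be added later, but one chosen after the data are seen carries less weight than one specified now.

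**Conclusion.** The point holds in conditional form. For continuous BCVA and CRT, the plan offers two analyses, names neither as main and includes no repeated-measures model. LOCF can overstate the Month 6 mean, and create an arm difference when dropout differs, if the effect fades and subjects leave after the peak. Its bias is about zero if the effect is sustained and dropout is random, and can be downward if exits come before the peak. Observed-case is sound only when dropout is unrelated to outcome.

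In the assumed scenario, the false differences run from about 0.5 to 1.2 letters wherever a planned analysis is biased, against about 0 for a likelihood model. At most this is 1.2/7.7, or about 16%, of the 95% half-width. All sizes rest on assumed dropout, SD and time course. The likelihood result also assumes that missingness can be explained by the data already observed, and the simulations did not include rescue.

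The documents do not support the inference that the formulation choice would turn on this. Selection draws on safety, tolerability and efficacy together, and the 15-letter endpoint and Kaplan-Meier analyses stand apart from LOCF. It is a modest, inexpensive improvement, best made before database lock.

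**What to change.** In SAP 13.1 and 13.2, name a mixed model for repeated measures as the main continuous analysis of BCVA and CRT. Include treatment, visit, treatment-by-visit, baseline and baseline-by-visit, with unstructured covariance and a named simpler structure if the model does not converge. Report the arm difference at each visit, including Month 6. Keep the existing LOCF and observed-case tables and label them as sensitivity analyses.

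State that the plan's post-rescue carry-forward rule still applies within the model, so carried-forward values remain for rescued subjects. Show the number of rescued subjects and of missing subjects by arm and visit, so that a reader can judge how much each matters.

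The cost is a little programming and possible non-convergence with about 40 subjects, which the fallback covers. No new visits, data or subjects are needed.
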